### **Statistical Analyses**

The statistical analysis of the data obtained from the study was evaluated using the IBM SPSS Statistics (version 22.0) package program. In order to evaluate the suitability of the data for normal distribution, One-Sample Kolmogorov-Smirnov test was conducted and kurtosis and skewness of the data was evaluated. Independent sample t-test was used to compare two independent groups among with normal distribution, dependent sample t-test and mixed design ANOVA were used to compare repeated measurements between two independent groups. All data have been provided with mean  $\pm$  standard deviation (mean $\pm$ SD). Mann-Whitney U test was used to compare data not showing normal distribution, and Wilcoxon test and Friedman test were used for repeated measurements between two groups. Categorical variables were compared using chi-square test and Fisher's exact chi-square test, and these data were shown with frequency (n, %) values. The significance level between the data was accepted as p=0.05. The graphical representations of the data were evaluated using the GraphPad Prism (version 9.3.0) package program.

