#### **Statical Analysis Plan**

#### Sample Size, Randomization and Formation of Groups

A power analysis was conducted to determine the number of participants to be included in the study. In order to exceed the 80% power level, it was determined that the study should be conducted with 50 individuals (25 participants in the training and 25 participants in the control group), at a significance level was set at 5% with an effect size of 0.518 (df=41; t=1.683) [1].

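### Wilcoxon and Friedman tests cannot compare the randomised arms, so an outcome judged non-normal has no stated between-arm test of change over time

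*SAP*

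**What the plan says.** The SAP's Statistical Analyses section describes two routes for continuous outcomes. The route depends on normality, assessed as follows: "One-Sample Kolmogorov-Smirnov test was conducted and kurtosis and skewness of the data was evaluated". The section gives no significance level for that test and no limits for skewness or kurtosis. It does not say whether arms, pooled data, single visits, changes or residuals are tested, or what happens when the criteria disagree. The software is the "IBM SPSS Statistics (version 22.0) package program", with no mention of whether the Kolmogorov-Smirnov (K-S) test is corrected for an estimated mean and SD.

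If data are judged normal, an independent t-test compares the groups, and "dependent sample t-test and mixed design ANOVA were used to compare repeated measurements between two independent groups".

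If not, the comparison of groups moves to ranks: "Mann-Whitney U test was used to compare data not showing normal distribution". Change over the visits is assigned to a different pair of rank procedures: "Wilcoxon test and Friedman test were used for repeated measurements between two groups".

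The sample-size section plans 25 participants per arm. The Protocol's Evaluation section sets measurements at baseline, week 12 and week 24.

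**The concern.** A randomised trial with a baseline and two later visits has to ask whether change differs between the arms. The SAP's two routes do not both answer that. The label attached to the rank tests says they work between groups, yet a signed-rank test on paired visits and a Friedman test across visits each describe one set of patients over time.

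Two things are at stake. An analyst who follows the text for a non-normal outcome may report one within-arm p-value per arm and treat significance in the training arm alone as an effect of training. And because the check that selects the route has no decision rule, two analysts could both comply with the SAP and yet answer different questions about the same outcome.

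**Working it through.** **Inputs.** From the documents: 25 per arm, three visits, 5% level. Assumed: two-sided tests, within-patient correlation 0.6, the size of the shared improvement, the skewed distributions and the skewness limits. The plan gives no figure of its own on this point to reproduce.

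**1. What each route can answer**

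| Question | Judged normal | Judged non-normal |
|---|---|---|
| Arms compared at one time | independent t-test | Mann-Whitney |
| Change within one arm | paired t-test | Wilcoxon, Friedman |
| Difference between arms in change | group-by-time term of mixed-design ANOVA | none stated |

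The last row is the gap.

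**2. One arm significant when both improve equally.** If each arm's within-arm test is significant with probability p, exactly one arm is significant with probability 2p(1 − p).

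*Two visits.* SD of change = √(2 × (1 − 0.6)) = 0.894 SD. Improvements of 0.3 and 0.5 SD become 0.335 and 0.559 standardised. With n = 25, paired-t power is 36.3% and 76.5%, so:
- 0.3 SD: 2 × 0.363 × 0.637 = 46%
- 0.5 SD: 2 × 0.765 × 0.235 = 36%

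Simulation with the Wilcoxon test itself gave 47% and 38%.

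*Friedman, three visits* (half the shift by week 12, all by week 24; 4,000 trials). Per-arm significance was 22.5% and 53.3%, so:
- 0.3 SD: 2 × 0.225 × 0.775 = 35%
- 0.5 SD: 2 × 0.533 × 0.467 = 50%

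The simulated values were 35% and 50%. In about half of these trials the significant arm was the training arm (17% and 25% of all trials).

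**3. How the normality check behaves.** Share of log-normal samples (log-SD 0.5) flagged, 20,000 samples per setting:

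| Criterion | n = 25 (one arm) | n = 50 (pooled) |
|---|---|---|
| K-S, uncorrected | 2% | 9% |
| K-S, corrected for estimated mean and SD | 42% | 71% |
| skewness beyond ±1 | 55% | 70% |
| skewness beyond ±2 | 12% | 14% |

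All these readings are compatible with the SAP. For truly normal data the corrected test flags 5% of samples. Across 2 arms × 3 visits, at least one flag occurs in 1 − 0.95⁶ = 26% of trials if the tests are independent, and in 24–25% in simulation. That rate applies only if the corrected test is run in all six cells and a single flag switches the outcome.

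**4. Type I error of the selected t-test or Mann-Whitney.** At 25 per arm, with normal and log-normal data (log-SD 0.5 and 1; 20,000 trials each), letting either K-S version choose the test gave 4.8–5.2%. Reporting the smaller of the two p-values every time gave 6.0–6.4%.

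**5. Where power comes from.** Illustrative setting: log-SD 0.6, 26% reduction, baseline correlation 0.5 or 0.7. Log-scale effect = −ln(0.74)/0.6 = 0.502. Log-scale ANCOVA divides the residual SD by 1/√(1 − ρ²), raising the effect to 0.579 or 0.703.

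| Analysis at 25 per arm | ρ = 0.5 | ρ = 0.7 |
|---|---|---|
| t-test, raw scale | 36% | 36% |
| Mann-Whitney | 39% | 38% |
| t-test, log scale, unadjusted | 41% | 40% |
| ANCOVA, raw scale | 43% | 57% |
| ANCOVA, log scale | 51% | 67–68% |

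The noncentral t gives 41% for the unadjusted log-scale test and 52% and 68% for log-scale ANCOVA, in agreement. Changing scale gains 2 points over Mann-Whitney; baseline adjustment then adds 10 points at ρ = 0.5 and 27–28 at ρ = 0.7.

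**The case against.** The best defence is that the rank route still contains a between-arm test. Mann-Whitney is named, and nothing forbids applying it to change scores. That stands as far as it goes: the arms can be compared at a visit. But the section assigns repeated measurements to Wilcoxon and Friedman and never links Mann-Whitney to change, so the comparison is left to the analyst.

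It can also be said that the SAP does not state that one-arm-only significance will be read as a treatment effect, and that the paired t-test on the normal route carries the same hazard. Both are true. The percentages in step 2 therefore measure the risk of a misreading that the between-groups label invites; they are not an error rate of the plan. The normal route differs in that mixed-design ANOVA is there to answer the right question.

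Three stronger readings are tempting and are not supported:

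- *The normality check is nearly blind, or fires by chance.* These describe two alternative versions of K-S, and the SAP does not say which is used. It also uses skewness and kurtosis, which can flag far more than uncorrected K-S. Testing by arm, and the six-cell false-flag rate, are assumptions.
- *Choosing the test from the data inflates false positives.* Applied mechanically to the arm comparison, it does not (step 4).
- *The choice between these tests is what costs power.* In the illustrative setting most of the gain comes from baseline adjustment, which is a separate merit of the remedy.

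**Conclusion.** The point holds in a limited form. For any continuous outcome judged non-normal, the SAP states no between-arm test of change over time, because the two tests it names for repeated measurements work within an arm. That follows from the text and needs no simulation. The rule that sends an outcome down this route is incomplete, so which question gets answered is open to the analyst's discretion.

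The size of the potential misreading rests on 25 per arm, correlation 0.6 and equal improvement of 0.3 to 0.5 SD. Under those assumptions a one-arm-only result is common, in roughly 35–50% of trials, although the arms do not differ. Other correlations or improvements would change the figure; with no improvement in either arm the Friedman figure is 10%. The documents give no outcome distributions, so how many outcomes would take the rank route is unknown. The validity of the t-test or Mann-Whitney comparison at a single visit is not in question here.

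**What to change.** Stop the normality check from choosing the test. Prespecify one baseline-adjusted between-arm model for every continuous outcome: for example, ANCOVA of the week-24 value on arm and baseline, with week 12 analysed the same way as secondary, or both visits in one repeated-measures model with baseline as a covariate.

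Name any outcomes to be analysed on the log scale before results are seen by arm. Add a rank-based ANCOVA as a sensitivity analysis, and inspect model residuals for information only. Keep Wilcoxon, Friedman and paired t-tests as within-arm descriptions, and state that they will not be used to compare arms.

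The cost is a rewritten paragraph and one sensitivity analysis, using data the Protocol already collects. The downside is that log-scale effects are reported as ratios, which need a sentence of explanation.

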The study was conducted in accordance with the Declaration of Helsinki with the document number E-10840098-772.02-2030 and permission dated 24.03.2022 from the Istanbul Medipol University Non-Interventional Clinical Research Ethics Committee. Informed Voluntary Consent Form was obtained from all volunteers participating in the study.

Research Protocol

The training protocol, duration and content of each training session were decided by doctors and diabetes dietitians. Individual trainings on carbohydrate counting were organized for patients in the training group in 3 sessions on different dates in parallel with carbohydrate counting training levels. The first level training session (90 minutes), provided basic information on nutrition and health and comprised of topics as, macronutrients in food groups and their effect on plasma glucose, glycemic index, healthy food preferences and meal planning, carbohydrate contents in various food items, concept of carbohydrate change (portions of foods containing 15 grams of carbohydrate) were taught. In the second session (45 minutes), the patients calculated the carbohydrate contents of the meals they consumed based on the knowledge from the previous session. In addition, the meal plans, snacking and main meal frequencies, physical activities, effect of insulin doses on plasma glucose, noted down by each patient in their data sheets of each patient were reviewed. In the third training (45 minutes), calculation of the total carbohydrate content of the consumed meal were repeated, in order to reinforce the patient's training in this field. Furthermore, the patients were informed about the Insulin Correction Factor and Carbohydrate/Insulin ratios, and the insulin doses to be taken per meal were calculated and exemplified based on their meal plan data sheets.

Evaluation

A questionnaire form containing sociodemographic information was completed by face-to-face interview method. In addition, biochemical (HbA1c, fasting plasma glucose (FPG), C peptide, total cholesterol, HDL, LDL, triglyceride, estimated glomerular filtration rate) and anthropometric and body composition (weight-height, BMI, fat mass, fat ratio, muscle mass, lean tissue mass, waist circumference), hand grip strength, blood pressure and physical activity measurements of the patients were taken at the beginning, 12th week and 24th week of the study.

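### Baseline is measured, but no planned test uses it as a covariate; a baseline-adjusted model would estimate the week-24 difference more precisely from data already collected

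*SAP*

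**What the plan says.** The Protocol's section headed Evaluation lists biochemical, body-composition, grip-strength, blood-pressure and physical-activity outcomes, and says "measurements of the patients were taken at the beginning, 12th week and 24th week of the study".

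For between-group work the SAP (Statistical Analyses) says "Independent sample t-test was used to compare two independent groups among with normal distribution". For repeated outcomes, "dependent sample t-test and mixed design ANOVA were used to compare repeated measurements between two independent groups". Non-normal outcomes go to Mann-Whitney, Wilcoxon and Friedman tests, and categorical ones to chi-square and Fisher tests. The section names no ANCOVA, regression or baseline-adjusted mixed model. It does not say whether the independent t-test is applied to visit values, changes or baseline characteristics, nor which ANOVA term is the treatment test.

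The sample-size section plans 25 per group "with an effect size of 0.518 (df=41; t=1.683"), aiming for power above 80%.

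**The concern.** Each planned route to the treatment effect handles baseline less well than it could.

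- **Independent t-test on visit values.** It ignores baseline, so any chance imbalance stays in the estimate.
- **Mixed-ANOVA group main effect.** It averages over all three visits, including the one before treatment could act, and so dilutes the effect.
- **Mixed-ANOVA group-by-time interaction.** It does use baseline, as a comparison of changes, so raw imbalance does not carry through. But a change score subtracts the whole baseline difference when only a fraction r of it is expected to persist, so it over-corrects. It is also a 2-df omnibus test that does not itself give the week-24 difference.
- **Missing visits.** Standard mixed-design ANOVA drops a patient with any visit missing.

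Type I error is not at stake. Precision is, and so is accuracy given the baseline imbalance that actually occurs. Both matter at 25 per arm.

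**Working it through.** **Inputs from the documents.** n = 25 per arm, d = 0.518 and a 5% level (SAP, sample size); three visits (Protocol, Evaluation).

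**Assumptions not in the documents.** Two-sided testing (t = 1.683 at df = 41 is the one-sided 5% critical value; the two-sided value is 2.020). The 0.518 is a difference in SDs of follow-up values. SD = 1 at each visit, the same correlation r between all visits (compound symmetry), complete data, and r from 0.3 to 0.8.

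**1. The plan's own figure.** By exact noncentral t, 80% power at d = 0.518 needs 47 per arm one-sided or 60 two-sided. With 25 per arm the power is 56% or 43%. So 50 does not reproduce as a two-group size; 25 reproduces only as a one-sided paired or one-sample n (80.8%). That is a separate matter, but it leaves the scale of 0.518 uncertain.

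**2. Precision at week 24.** With 2/n = 0.08, the SE is:

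- unadjusted: √0.08 = 0.283, so the half-width is 2.011 × 0.283 = 0.57 (df 48)
- change score: √[0.08 × 2(1 − r)] (df 48)
- ANCOVA: √[0.08 × (1 − r²)] (df 47)

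At r = 0.7, ANCOVA gives √(0.08 × 0.51) = 0.202, and 2.012 × 0.202 = 0.41. The ratio of ANCOVA variance to change-score variance is (1 + r)/2, which is below 1 for any r < 1.

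| 95% CI half-width (SD) | r=0.3 | 0.5 | 0.6 | 0.7 | 0.8 |
|---|---|---|---|---|---|
| Unadjusted | 0.57 | 0.57 | 0.57 | 0.57 | 0.57 |
| Change score | 0.67 | 0.57 | 0.51 | 0.44 | 0.36 |
| ANCOVA | 0.54 | 0.49 | 0.46 | 0.41 | 0.34 |

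**3. Power at d = 0.518.**

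- Week-24 t-test: noncentral t, df 48.
- Main effect: difference 2d/3 (constant effect) or d/2 (half the effect at week 12), variance 0.08(1 + 2r)/3.
- Interaction: noncentral F(2, 96), λ = (n/2) × SS/(1 − r), where SS = (2/3)d² (constant) or d²/2 (half at week 12).
- ANCOVA: F(1, 47), λ = (n/2)d²/(1 − r²).

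At r = 0.7 with a constant effect, the interaction has λ = 12.5 × 0.667 × 0.2683/0.3 = 7.45, and ANCOVA has λ = 12.5 × 0.2683/0.51 = 6.58 on one numerator df.

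| Power (%) | r=0.3 | 0.5 | 0.6 | 0.7 | 0.8 |
|---|---|---|---|---|---|
| Week-24 t-test | 43 | 43 | 43 | 43 | 43 |
| Week-24 ANCOVA | 47 | 54 | 61 | 71 | 85 |
| *Constant effect:* main effect | 37 | 31 | 29 | 27 | 25 |
| Interaction | 33 | 45 | 54 | 67 | 85 |
| ANCOVA gain over interaction (points) | 14 | 10 | 7 | 4 | 0 |
| *Half effect at week 12:* main effect | 23 | 20 | 18 | 17 | 16 |
| Interaction | 26 | 34 | 42 | 54 | 73 |
| ANCOVA gain over interaction (points) | 21 | 20 | 19 | 17 | 12 |

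Simulation of the constant-effect case (20,000 trials per setting) agreed to within about 1 point.

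**4. Chance imbalance.** The baseline difference has SE √0.08 = 0.283 SD. A one-SE imbalance shifts the unadjusted week-24 difference by r × 0.283 = 0.08/0.14/0.17/0.20/0.23 SD, and a change comparison the other way by (1 − r) × 0.283 = 0.20/0.14/0.11/0.08/0.06 SD.

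**5. Missing visits.** No rate is given. If 10% missed each follow-up visit independently, 25 × 0.9² = 20.25 per arm would be complete. At 20 per arm the interaction's power (constant effect) falls to 27/36/44/56/75%. A week-24 ANCOVA also loses patients: at 22.5 per arm its power is 50/66/81% at r = 0.5/0.7/0.8.

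**The case against.** The strongest reply is that the SAP already assigns repeated outcomes to the mixed ANOVA, whose interaction uses baseline. The independent t-test may be meant only for single-time comparisons, and nobody may intend the main effect as the efficacy test. Against the interaction, the constant-effect gain is only 4 points at r = 0.7 and none at 0.8. This stands, and it is why the case rests on week-24 precision rather than power.

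The power figures also depend on compound symmetry. If correlation decays between visits (AR(1), constant effect, simulated), the interaction can beat week-24 ANCOVA. At adjacent r = 0.8 it has 72% power uncorrected, or 69% with Greenhouse-Geisser correction, against 64%. At 0.9 the corrected figure is 94%, against 86%. This stands too. However, the interaction still gives no week-24 estimate, and the average of weeks 12 and 24 from a baseline-adjusted model has 82% power at adjacent r = 0.8. Under compound symmetry and a constant effect that average has 67/72/77/85/94%, above the interaction throughout.

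The scale of 0.518 is also uncertain. If it is in SDs of change, the interaction has 45% power at every r and ANCOVA has 54/52/49/47% at r = 0.5/0.6/0.7/0.8. The gains are then 10/7/5/3 points and the high absolute powers disappear. The precision table does not depend on d.

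Finally, this is an improvement in efficiency and not an error in the plan. That is agreed.

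**Conclusion.** The point holds. Baseline is collected and no planned method adjusts for it. For the week-24 difference, ANCOVA gives the narrowest interval at every r from 0.3 to 0.8. Its SE is below the unadjusted one by 13%, 29% and 40% at r = 0.5, 0.7 and 0.8, and below the change-score one by 13%, 8% and 5%. At r near 0 there is nothing to gain.

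The power advantage over the interaction is conditional: modest to nil with a constant effect and high r, larger if the effect builds up, and negative in some serial-correlation settings. Confidence is high for the missing covariate and the precision gain. The power figures are only as firm as the assumed correlation pattern, effect scale and time course. This is a change that should be made, not one on which the trial's validity depends.

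**What to change.** In the SAP's Statistical Analyses section, make the between-group analysis of each continuous outcome measured at baseline a linear mixed model of the week-12 and week-24 values, with baseline as covariate and terms for arm, visit and arm-by-visit. Report the adjusted week-24 difference with its 95% CI. This keeps patients who miss one follow-up visit. With complete data, a week-24 ANCOVA on arm and baseline is a simpler alternative.

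State which values any remaining independent t-test is applied to. Say how outcomes now routed to the rank tests will be handled, for example by transformation before the same model, since those tests do not adjust for baseline either.

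The cost is SAP wording: no new data or visits, and both models are available in the SPSS version named (MIXED or UNIANOVA). The SAP is written in the past tense and the Protocol's recruitment period runs to December 2024, so if outcome data have already been analysed, the change should be declared as post hoc. Choosing a single primary outcome and correcting the sample size are separate matters that this change does not settle.

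### The planned mixed-design ANOVA would normally keep only patients seen at weeks 0, 12 and 24, which costs precision and can bias the arm comparison if response-related withdrawal affects the two arms differently

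*SAP*

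**What the plan says.** The Protocol (Evaluation) schedules three assessments: "measurements of the patients were taken at the beginning, 12th week and 24th week of the study". The SAP (Sample Size, Randomization and Formation of Groups) states that "the study should be conducted with 50 individuals (25 participants in the training and 25 participants in the control group" arm, and shows no allowance for dropout.

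The SAP (Statistical Analyses) divides the tests as follows.
- Single-time comparisons of the arms: "Independent sample t-test was used to compare two independent groups among with normal distribution" and, for other data, "Mann-Whitney U test was used to compare data not showing normal distribution".
- Repeated measurements, normal data: "dependent sample t-test and mixed design ANOVA were used to compare repeated measurements between two independent groups".
- Repeated measurements, other data: "Wilcoxon test and Friedman test were used for repeated measurements between two groups".

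The analysis is "evaluated using the IBM SPSS Statistics (version 22.0) package program", but the SPSS procedure is not named. The text available for review contains no analysis population, intention-to-treat statement, missing-data rule or sensitivity analysis.

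**The concern.** The dependent t-test, Wilcoxon and Friedman tests are within-patient tests. That leaves mixed-design ANOVA as the only named repeated-measures method that sets one arm against the other. Run in the usual way it works on complete rows, so one missed visit removes the patient, together with results already in hand.

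The arm comparison would then be one of patients who completed every visit. The arms also carry different burdens. The Protocol (Research Protocol) says "Individual trainings on carbohydrate counting were organized for patients in the training group in 3 sessions on different dates", lasting 90, 45 and 45 minutes, and only those patients are taught carbohydrate and per-meal insulin calculation. Withdrawal that differs by arm and is related to progress is therefore plausible, although the documents neither measure nor predict it. With 25 per arm, a handful of such patients can move the estimate, and the week-12 values that would reveal it would be left out of the analysis.

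**Working it through.** **Plan's own figure.** The plan gives no dropout or missing-data figure to reproduce. Its sample size does not decide this point. For orientation, a two-arm t-test with effect size 0.518 and 25 per arm has 56% power one-sided and 43% two-sided. At 10%, 20% or 30% loss (about 22, 20 or 18 per arm) the one-sided figure falls to 52%, 49% or 45%.

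**Loss of patients.** Assume 10% miss each follow-up visit independently. The share with at least one gap is 1 - 0.9² = 0.19, so 25 × 0.81 = 20.25 per arm stay in the ANOVA.

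**Loss of precision.** Assume SD 1.2 and correlation 0.6 between visits.
- SE of the arm difference in change, full data: √(2 × 2 × 1.2² × (1 - 0.6) / 25) = √0.0922 = 0.304.
- With 20.25 per arm: 0.304 × √(25/20.25) = 0.304 × 1.11 = 0.34.
- SE of the raw week-24 difference, full data: √(2 × 1.2² / 25) = √0.1152 = 0.339. This is larger than 0.304, so the choice of contrast matters for the fix.
- With 20% random loss after week 12 in both arms, simulated trials gave an SE of 0.343 for completers and 0.335 for a likelihood estimate, about 2% smaller. The gain is modest for this pattern.

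**Why selection on week-12 change carries over.** With equal SD σ and equal correlation ρ, the covariance of the week-12 and week-24 changes is σ²(1 - ρ), and the variance of the week-12 change is 2σ²(1 - ρ). The slope is 0.5, so half of any shift in completers' week-12 change appears in their week-24 change.

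**Bias, HbA1c points.** Assumed: SD 1.2, correlation 0.6, true difference -0.5. Where loss is related to week-12 change, patients who had not improved are more likely to leave, at log-odds 1 to 1.5 per SD.

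| Loss, training/control | Related to week-12 change? | Completers | Likelihood estimate |
|---|---|---|---|
| 24%/8% | no | -0.50 | -0.50 |
| 24%/8% | yes, both arms | -0.57 to -0.60 | about -0.50 |
| 32%/8% | no | -0.50 | -0.50 |
| 32%/8% | yes, both arms | -0.60 to -0.64 | about -0.50 |
| 20%/20% | yes, same in both arms | -0.50 | -0.50 |

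Overstatement: 0.07/0.5 = 14% to 0.10/0.5 = 20% in the second row, and 0.10/0.5 = 20% to 0.14/0.5 = 28% in the fourth.

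**Bias, SD units.** Assumed: true effect -0.518, correlation 0.5 or 0.7, loss depending on week-12 change.

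| Loss, training/control | Mechanism | Completers | Likelihood estimate |
|---|---|---|---|
| 30%/10% | unrelated | -0.518 to -0.519 | -0.518 |
| 30%/10% | poor responders leave, both arms | -0.571 to -0.631 | -0.514 to -0.519 |
| 30%/10% | selective in training only | -0.644 to -0.704 | -0.515 to -0.517 |
| 20%/20% | same in both arms | -0.519 to -0.520 | -0.519 to -0.520 |
| 20%/20% | opposite in the two arms | -0.694 to -0.780 | -0.516 to -0.521 |

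**Other mechanisms, unequal loss (5%/15%, 20%/10%, 30%/10%), SD units.**
- Loss depending on the week-12 level: no material bias in completers (at most 0.004).
- Loss depending on the baseline level: completers are off by 0.025 to 0.084, and the benefit is understated when training loses more. The likelihood estimate is off by at most 0.005.
- Loss depending on the unseen week-24 value: completers are off by 0.024 to 0.080 and the likelihood estimate by 0.037 to 0.115. Neither is protected, and here the likelihood estimate is the further off.

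**The case against.** Five objections deserve weight.

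1. A reader might infer that unequal withdrawal in itself biases the training effect. It does not: 24%/8%, 32%/8% and 30%/10% loss unrelated to response all left the estimate where it should be. Nor are equal rates a safeguard, as the opposite-mechanism rows show.

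2. A reader might infer that the SAP orders incomplete patients to be dropped. It does not say so. It names a method and a package, and a model called mixed-design ANOVA could be fitted in a way that keeps partial data. What stands is that the usual form is complete-case and nothing in the available text says otherwise.

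3. The harm is partly contained. A patient who misses only week 12 can still enter a week-24 independent t-test or Mann-Whitney comparison. One who leaves before week 24 cannot. The SAP does not say which test governs.

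4. The quantity simulated, the completers' difference in change to week 24, is not named in the SAP. It is one component of the arm-by-time comparison that the ANOVA tests. All dropout rates, SDs, correlations and selection strengths are assumed, and a bias of about 0.1 point is only about 0.3 of an SE near 0.34.

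5. The scenarios that favour the likelihood model have loss driven by observed values, which it handles by construction. Under missing-not-at-random loss it is not a cure.

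Objections 1 and 2 set the limits of the claim. Objections 3 and 4 keep its size modest. Objection 5 means that a sensitivity analysis must accompany the change. None of them supplies a reason to prefer the complete-case ANOVA as the main analysis.

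**Conclusion.** The point holds in this form. The only named repeated-measures comparison of the arms would, as usually run, be restricted to patients with all three visits. That discards observed data and costs precision. It can also bias the arm difference in change when response-related withdrawal distorts the arms differently, through its rate or its mechanism.

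Under the stated assumptions the overstatement is about 14% to 20% at 24%/8% loss and 20% to 28% at 32%/8%. It is nil when loss is unrelated to response, or when rate and mechanism match across arms. The direction is not fixed: loss driven by baseline level can understate the benefit. The documents do not show that differential withdrawal occurred or was expected, so they support a claim of avoidable risk and not of a biased result. Because the remedy is cheap, the change should be made. Confidence is medium, since the size depends on withdrawal that the documents do not describe.

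**What to change.** In the SAP, Statistical Analyses:
- Replace mixed-design ANOVA with a likelihood-based linear mixed model (SPSS MIXED). Use fixed effects for arm, visit and arm-by-visit, and an unstructured covariance over weeks 0, 12 and 24. Include every randomised patient in the allocated arm and every observed visit.
- Take the arm difference in change from baseline to week 24, or constrain the baseline means to be equal across arms. Do not take the raw week-24 contrast with baseline left free: with full data its SE is 0.339 against 0.304 for change under the inputs above.
- Report the number missing each visit, with reasons, by arm.
- Keep the complete-case ANOVA as a sensitivity analysis.
- Add a simple missing-not-at-random sensitivity analysis, for example shifting the unobserved week-24 values by a range of amounts, in the training arm alone and in both arms.

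There is no need for every test to use the same patients, which would conflict with keeping all observed visits. The change does not repair the non-normal branch, where Wilcoxon and Friedman do not compare the arms at all.

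**Cost.** SAP wording and one procedure in the package already named, with no added visit or measurement. The model relies on data being missing at random. An unstructured covariance over three visits has 3 × 4 / 2 = 6 parameters against 2 for compound symmetry, so 4 more are estimated. If almost nobody withdraws, the result will barely change. If the data have already been analysed, the change should be labelled as made afterwards.
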